5.1.1.3 Follow-up cohort for evaluating the exploratory research objective

The goal of the post-initiation exploratory analysis is to evaluate the frequency of attacks after initiation of prophylactic therapy, understand utilization, and determine how many months patients were attack free after initiation. This analysis will not directly influence the cost-effectiveness model; however, there is value in exploring these patient-relevant outcomes in real-world data.

The follow-up cohort will be derived from the baseline cohort. In addition to the baseline cohort inclusion criteria, all patients will be required to have a minimum of 90 days eligibility in the follow-up period. As in the baseline cohort, patients initiating Cinryze will be further required to have recurring use during the 90 days following cohort entry to confirm prophylactic use. Patients will be censored upon maximum follow-up of 365 days, disenrollment, the end of data (March 31st, 2020), or death, whichever comes first. Thus, patients will contribute a minimum of 3 months and a maximum of 1 year of follow-up time to the analysis. A one-year maximum follow-up was selected due to the recency of the Takhzyro approval (August 23rd, 2018).

5.1.1.4 Dose reduction cohort evaluating the exploratory research objective

[figure not shown]
The dose reduction exploratory cohort will only focus on patients initiating Takhzyro.

Patients will be eligible to enter the cohort on initiation of Takhzyro, during August 23, 2018 through July 5, 2019 (Figure 2). August 23, 2018 was selected as the start of the study period based on the approval date for Takhzyro. New use will be defined as no use of Takhzyro, during the 180 days prior to initiation (washout period). Each patient will be included only once, on the first qualifying event. Patients will be required to be continuously enrolled in the 180 days prior to

initiation and for at least 270 days post cohort entry. The FDA label for Takhzyro, states that patients whose attacks are well-controlled for six months should reduce dosing to every four weeks, thus the cohort will require a minimum of six months follow up plus 90 days to establish the new dosing regimen. To be included in the cohort, patients will be required to have dosing, on average, every two weeks during the 180 days post cohort entry.

Using the dose reduction cohort, we will determine the percent of patients that receive the less frequent dosing regimen after six months attack free.

Figure 2: Takhzyro dose reduction study diagram

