- Health care resource utilization and cost inputs were used from published observational studies that were published up to 10 years ago. Revising these estimates with updated RWE could impact the drugs' cost-effectiveness.

The objectives of this observational RWE study are focused on addressing these uncertainties and generating updated cost-effectiveness model inputs. The following research objectives will be addressed:

Primary Objective. Describe baseline demographic characteristics, attack rates, and attack-related medical service utilization among initiators of one of the three treatments for long-term prophylaxis use (Takhzyro, Haegarda, or Cinryze).

- What is the HAE baseline attack rate per month (stratified by severity) in the six months pre-initiation?
- Where is on-demand treatment for acute attacks administered? What is the distribution of specific drugs? How many prescriptions do patients receive?
- For patients with severe attacks, what percent end up hospitalized, and within these patients, what is the utilization of procedures such as cricothyrotomy/tracheotomy, intubation, and artificial respiration?
- What are the costs associated with medical utilization during the acute attack?

Exploratory Objective: Explore attack rates and utilization following long-term prophylaxis initiation.

- What is the severe attack rate per month, post-initiation?
- What percent of patients are attack-free during the follow up period?

- What are the utilization patterns of the prophylactic medications, post initiation?
- What percent of patients receive less frequent dosing for Takhzyro after six months attack free (in line with FDA recommendations)? Do any patients titrate down prior to six months?

5. Research methods

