5.4.1.3 Exploratory Follow-up descriptive analyses

Due to the small sample size, there is a lack of power to complete a formal pre/post analysis to detect a meaningful difference in attack rates. Thus, our follow-up analysis will be descriptive.

In the follow up period, we are interested in exploring the frequency of attacks after initiation of prophylaxis therapy, understanding utilization, and determining how many months patients were attack free after initiation. Follow up attack rates will be stratified by drug (Takhzyro, Haegarda, and Cinryze) and we will focus on severe attacks only. We will explore the following:

- Adherence to prophylaxis therapy
- Switching behavior between the three prophylaxis drugs
- Attack rates, including attack-free months

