Pharmacy – on-demand drug utilization (# of scripts and total dose)			-	

Table 3: Descriptive analysis during follow-up (post initiation of prophylaxis)

Characteristic	Takhzyro initiators	Haegarda initiators	Cinryze initiators*	Notes
Mean age at initiation				
Female, %				

Distribution of severe attack free months				
Mean attack rate per month – severe-HAE specific- follow up period				
Proportion of patients with PDC >80%				
Switching- % patients switching to Takhzyro	N/A			
Switching- % patients switching to Haegarda		N/A		
Switching- % patients switching to Cinryze			N/A	

*Cinryze patients were required to be adherent to therapy in the 90 days post initiation to determine that they were taking Cinryze prophylactically (versus on-demand use). Takhzyro and Haegarda patients were not required to demonstrate adherence in the 90 days post initiation.

Table 4: Exploratory dose reduction outcomes

Characteristic	Takhzyro initiators	Notes
Percent of Takhzyro patients attack free for 6-month period		
Percent patients on every 4-week dosing for 6 months		
Percent of patients that titrated down to every 2-week dosing		

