Annex 4: United Healthcare HAE Drug Coverage Policies

	Takhzyro ³⁹	Cinryze ⁴⁰	Haegarda ⁴¹
Attack rate requirement	At least 1 attack every 4 weeks	Prescriber attests that patient has experienced attacks of a severity and/or frequency such that they would clinically benefit from prophylactic therapy with Cinryze	Prescriber attests that patient has experienced attacks of a severity and/or frequency such that they would clinically benefit from prophylactic therapy with Haegarda

		AND Submission of medical records documenting a history of failure, contraindication, or intolerance to Haegarda (C1 esterase inhibitor, human)	
Reauthorization	Every 8 months	Every 12 months	Every 12 months
Dose changes	If no acute attacks in previous 6 months move to 300 mg every 4 weeks for 12 months	--	--

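### The Takhzyro dose-reduction cohort screens out the early down-titrators that section 4 asks about, and Table 4's six-month row does not match the 90-day definition or the 270-day minimum follow-up

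*Protocol*

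**What the plan says.** Section 4 lists two dose-reduction questions under the exploratory objective: what share of Takhzyro patients go to less frequent dosing after six attack-free months, and "Do any patients titrate down prior to six months".

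Section 5.1.1.4 defines the only cohort built for dose reduction. Entry runs from 23 August 2018 to 5 July 2019. Patients must be enrolled for 180 days before "initiation and for at least 270 days post cohort entry". The length is explained by the label's six-month condition, "thus the cohort will require a minimum of six months follow up plus 90 days to establish the new dosing regimen". To be included, "patients will be required to have dosing, on average, every two weeks during the 180 days post cohort entry". No tolerance around that average is given.

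Annex 2 identifies four-weekly administration by a total of at most 1200 mg over 90 days.

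Besides a row on being attack free, Table 4 in Annex 3 has two dosing rows: "Percent patients on every 4-week dosing for 6 months" and "Percent of patients that titrated down to every 2-week dosing". Table 3, for the general follow-up cohort, covers severe attacks, adherence and switching between drugs, but has no row on dosing interval.

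**The concern.** Two things do not fit together.

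First, whether patients reduce before six months is put to a protocol whose only dose-reduction cohort requires that they did not. The result would be close to zero because of the entry rule, yet could be read as evidence on practice. The Table 4 row that looks meant for this question refers to moving down to the interval that all members must already be on.

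Second, Table 4 promises a six-month duration on the reduced schedule, while the measurement definition and the guaranteed follow-up cover 90 days of it. Without a stated denominator, patients who cannot be observed long enough would either count as not persisting or be scored on 90 days under a six-month label.

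Section 4 names the share of patients who switch to the less frequent dose and stay on it as one of three uncertainties behind the study, and says that it could affect incremental cost-effectiveness.

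**Working it through.** **Inputs.** Entry window 23 August 2018 to 5 July 2019, two-weekly rule over 180 days, and minimum follow-up of 270 days (section 5.1.1.4); end of data 31 March 2020 (section 5.1.1.3); 90-day measure of four-weekly dosing (Annex 2); six-month row (Table 4).

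**1. The plan's own figure.** 180 + 90 = 270 days, and 5 July 2019 + 270 days = 31 March 2020. The minimum follow-up and the last entry date agree exactly with the end of data.

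**2. Does the entry rule admit early reducers?** For a patient who goes from 14-day to 28-day dosing at day t, the mean interval over 180 days is 180 / (t/14 + (180 − t)/28).

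| Change at day | Calculation | Mean interval (days) |
|---|---|---|
| none | 180 / 12.86 | 14.0 |
| 150 | 180 / 11.79 | 15.3 |
| 120 | 180 / 10.71 | 16.8 |
| 90 | 180 / 9.64 | 18.7 |
| 60 | 180 / 8.57 | 21.0 |

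A change by day 120 fails a two-weekly average clearly. A change in the last weeks before day 180 might pass, depending on the unstated tolerance. The cohort therefore excludes nearly all early reducers.

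**3. Is the question answered elsewhere?** Section 5.1.1.3 sets no two-weekly rule for Takhzyro patients in the general follow-up cohort, but that section does not take up the early-reduction question and Table 3 has no row for it.

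**4. Can six months of four-weekly dosing be seen?**
- Needed: 180 + 180 = 360 days. Guaranteed: 270 days, which leaves 270 − 180 = 90 days after day 180, so 90 days short.
- Time from entry to the end of data: 586 days for the first entry date, 270 for the last.
- Last entry date that allows 360 days: 31 March 2020 − 360 days = 6 April 2019.
- Entry dates that allow it: 227 of 317 (71.6%). Entry dates from 7 April to 5 July 2019: 317 − 227 = 90 of 317 (28.4%).
- If the whole cohort is the denominator and entry is uniform, the row could not exceed about 72% even if every patient reduced at day 180, stayed on the new interval and stayed enrolled.

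**The case against.** The strongest defence is that the two-weekly rule is a coherent baseline for the purpose section 5.1.1.4 states, namely the share reducing after six attack-free months. Section 4 does not assign the early question to this cohort, and the follow-up cohort, which is meant to describe utilization for up to 365 days, could supply it. That stands as a defence of the rule for the later question. It does not supply an answer to the early one, because no cohort, definition or table row is attached to it. The row naming the two-weekly interval may be a slip, but correcting its wording would leave the entry rule in place.

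It is also fair that 270 days is a floor with no stated ceiling for this cohort. A reader might infer that six-month persistence cannot be observed at all. The documents do not support that: entrants up to 6 April 2019 can reach 360 days. If the 365-day cap of section 5.1.1.3 applied here too, 365 − 180 = 185 days would still remain.

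Two further inferences are tempting.
- That late reducers are counted as non-reducers. This holds only if the 90-day window is fixed at days 181 to 270. Neither section 5.1.1.4 nor Annex 2 says so, and Figure 2 is not shown in the text at hand. The eight-month reauthorization in Annex 4 cannot establish when patients reduced, because the policy cited was updated in September 2020, after the data end.
- That attack free in Table 4 ignores non-severe attacks. The statement "we will focus on severe attacks only" in section 5.4.1.3 concerns follow-up rates by drug. Table 3 specifies severe attacks and Table 4 does not, so the term is undefined there rather than shown to be severe-only.

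**Conclusion.** The point holds in two parts. As built, the dose-reduction cohort cannot answer the early down-titration question beyond a small tolerance effect near day 180, and nothing else in the protocol is assigned to answer it; one Table 4 row also contradicts the entry rule. The six-month row conflicts with the 90-day definition and with the guaranteed follow-up. It cannot be evaluated for patients entering on the last 90 of 317 entry dates, or for anyone disenrolled before about day 360.

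The 72% and 28% shares are of entry dates. They become shares of patients only if entry is uniform, and disenrolment would lower the evaluable share. The interval figures assume a clean change from 14 to 28 days.

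Severity is moderate. The objective is exploratory, no primary result is touched, and section 5.1.1.3 says that the post-initiation analysis will not directly influence the cost-effectiveness model. Nothing here judges which dosing interval is right; the passages need to be reconciled.

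**What to change.** 1. Estimate early reduction in all Takhzyro initiators with at least 180 days of follow-up, without the two-weekly entry rule, and give it its own row. Two details need stating. On a 90-day measure, a patient with only 180 days can be confirmed only if the reduction began by day 180 − 90 = 90, so the confirmation window should run past day 180 where follow-up allows. And because the Annex 2 definition has an upper dose limit but no lower one, patients who stop or switch must be separated from those who reduce.
2. Keep the two-weekly cohort for reduction after day 180, using the Annex 2 90-day definition.
3. Report six-month persistence only in patients with at least about 360 days of follow-up, and state that denominator.
4. Reconcile the two Table 4 dosing rows with section 4, section 5.1.1.4 and Annex 2.
5. Optionally, state where the 90-day window may fall after day 180, and whether attack free includes non-severe attacks.

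The cost is wording in section 5.1.1.4 and Table 4 and one further descriptive estimate from the same data. The persistence row will rest on fewer patients, drawn from about 72% of the entry window. A cumulative incidence curve with stopping or switching as competing events would be a refinement but is not needed to cure the problem.

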Android Methitest Testred Virilon (Methyltestosterone)	NDCs: 00187-0902-01 00115-1408-01 00187-0901-01 00115-7037-01	Clinical Pharmacology Database²⁰
Winstrol (Stanozolol)	NDCs: 0024-2253-04??	Clinical Pharmacology Database²⁰
Prophylactic use of Cinryze and Ruconest	Algorithm and code lists	Source
Cinryze prophylactic use	Cinryze is indicated for prophylaxis, but is used off-label for acute attacks. Prophylactic use will be defined as continuous refills of Cinryze averaging ≥ 1500 IU/week for ≥ 90 days.	Riedl 2018²²
Ruconest prophylactic use	Ruconest is indicated for on-demand use, but is used off-label for prophylaxis. Patients with Ruconest prophylactic use will be excluded from the cohort. Prophylaxis use will be defined as continuous refills of Ruconest averaging 50 IU/kg once weekly for 90 days.	Riedl 2018²²
every four-week	Used to determine if a dose reduction occurred.	

administration of Takhzyro	This will be measured over a 90-day follow-up period based on total dose <= 1200 mg over that period. The 1200 mg is based on three 300 mg injections plus one additional injection to account for potential variation in exact timing.	
Attack severity	Algorithm and code lists	Source
Severe	
ED visit with/without hospitalization, identified based on “Type of service” coded as inpatient or emergency room. Events identified as HAE-specific include at least one of the following diagnose (as a primary diagnosis for hospitalizations /or treatments indicative of an attack:
 
 € Codes often associated with HAE: ICD-9-CM 277.6 or ICD-10-CM D84.1 € Angioedema diagnosis: ICD-9-CM 995.1 or ICD-10-CM T78.3* € Administration of on-demand HAE treatment € Diagnosis of swelling, abdominal pain, or asphyxiation: 
 o ICD-9-CM 518.81, 518.84, 787.0*, 782.2, 789.0*, 786.02, 786.05, 786.1 o ICD-10-CM J96.0*, J96.2*, J96.9*, R06.0*, R06.1, R10.*, R11.*, R22.0*, R22.1, R19.0 	
UpToDate states severe attacks are treated in ED.²³
 
Tachdjian 2020¹
 
Zilberberg 2010²⁴
 
Longhurst & Bork, 2019

Non- severe attack	
Each dose of an on-demand therapy over two acute attack doses is considered an attack. The number of doses dispensed will be calculated from the quantity dispensed and recommended dose and
 
Any on-demand therapy administered outside an inpatient or emergency room setting will be considered a non-severe attack.
	
Utilization	Algorithm and code lists	Source

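### The only cohort built to measure Takhzyro dose reduction filters out patients who reduce before six months, so a stated exploratory question has no valid denominator

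*Protocol*

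**What the plan says.** Section 4 of the protocol lists two Takhzyro dosing questions under the exploratory objective. One is the percentage who move to less frequent dosing after six months free of attacks. The other is "Do any patients titrate down prior to six months".

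Section 5.1.1.4 defines one dose reduction cohort. Enrolment must cover the 180 days before "initiation and for at least 270 days post cohort entry". In addition, "patients will be required to have dosing, on average, every two weeks during the 180 days post cohort entry". The section states no tolerance around that average. It gives the cohort one output: "we will determine the percent of patients that receive the less frequent dosing regimen after six months attack free".

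Annex 2 defines four-weekly administration: "This will be measured over a 90-day follow-up period based on total dose <= 1200 mg over that period". Its basis is also given: "The 1200 mg is based on three 300 mg injections plus one additional injection to account for potential variation in exact timing".

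In Annex 3, the only row on titration is in Table 4: "Percent of patients that titrated down to every 2-week dosing". Annex 1 lists every two weeks as the starting interval. Table 3, for the follow-up cohort, covers severe attacks, proportion of days covered and switching, but not the dosing interval.

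**The concern.** A patient who lengthens the interval before day 180 receives fewer injections in the first 180 days and so tends to fail the entry criterion. The criterion thus selects on the event that the second question asks about. It takes early reducers out of both numerator and denominator.

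If the early question is nevertheless answered in this cohort, a figure at or near zero could be taken to mean that early reduction does not happen, when such patients were simply not admitted. If it is not answered there, the protocol names no group in which it would be. Either way a stated research question lacks a valid analysis.

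**Working it through.** **Inputs.** Annex 1: 300 mg per injection, every two weeks at first, every four weeks after reduction. Section 5.1.1.4: averaging over 180 days and 270 days of enrolment after entry. Annex 2: at most 1200 mg in 90 days.

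**Assumptions.** Injections fall exactly on schedule from day 0. There is one change from 14-day to 28-day intervals, which starts at the first injection on or after the change day and is sustained. Average interval = 180 / (injections on days 0-179).

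**Step 1: the plan's own figures.** 3 x 300 mg + 300 mg = 1200 mg, that is, 4 injections, and 90/28 = 3.2, so the threshold reproduces. 5 July 2019 + 270 days = 31 March 2020, the end of data, so the entry window also reproduces.

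**Step 2: average interval by change day.** Full two-weekly dosing gives injections on days 0, 14, ..., 168, which is 13, and 180/13 = 13.8 days.

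| Change day | Injections, days 0-179 | Average interval (days) |
|---|---|---|
| 28 | 8 | 22.5 |
| 56 | 9 | 20.0 |
| 84 | 10 | 18.0 |
| 112 | 11 | 16.4 |
| 140 | 12 | 15.0 |
| 168 | 13 | 13.8 |

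**Step 3: entry together with the Annex 2 rule.** At 14-day spacing the first 90 days hold at most 7 injections (days 0 to 84). Because intervals only lengthen, a patient with at most 4 injections in some 90-day window inside the 180 days has at most 4 in the last 90 days. The total is at most 7 + 4 = 11, and 180/11 = 16.4 days. So under any cut-off of 16 days or less, nobody with this dosing pattern can both enter and meet the rule before day 180.

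**Step 4: dependence on the missing tolerance.** For illustration, spread change days evenly over days 28-179 (152 days; an assumption).

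| Cut-off on the average | Earliest change day admitted | Change days admitted | Admitted and meeting the rule before day 180 |
|---|---|---|---|
| 14 days | 155 | 25 (16%) | 0 |
| 15 or 16 days | 127 | 53 (35%) | 0 |
| 17 days | 99 | 81 (53%) | 28 (18%) |
| 18 days | 71 | 109 (72%) | 56 (37%) |
| 21 days | 43 | 137 (90%) | 84 (55%) |
| no criterion | - | 152 (100%) | 99 (65%) |

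The last row separates two effects. Even without the criterion, 53 of 152 change days (35%), those after day 126, cannot show 4 or fewer injections in 90 days by day 180. All 152 meet the rule by day 270. The remaining loss in the other rows comes from the criterion.

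**Step 5: where the admitted early reducers go.** Patients who change between day 127 or 155 and day 179 can enter under a tight cut-off, and they meet the 90-day rule only with time after day 180. Unless the change is dated, they would be counted as reducing after six months.

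**The case against.** The strongest reply is that section 5.1.1.4 never assigns the early question to this cohort. Its one stated output is the percentage reducing after six months, and for that a two-weekly run-in is a sensible denominator. This stands. A reader might infer that the protocol commits itself to reporting that almost nobody reduces early, but the text does not say so. What it shows is a question whose only plausible cohort excludes the relevant patients.

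A reader might also infer that no early change at all can pass a strict two-weekly average. That is not so: with whole injections, changes from day 155 pass. How many more pass depends on a tolerance the protocol does not state.

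It can be said that the follow-up cohort (section 5.1.1.3) has no two-weekly criterion for Takhzyro, and that section 5.2.1.7 plans total prophylaxis dose and proportion of days covered. Lower drug use would therefore not be invisible. But these measures neither date a change nor separate a new regimen from missed doses, and Table 3 has no row for it.

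The Table 4 titration row may have been meant for this question. As worded it names the interval that Annex 1 gives as the starting one, so it does not measure reduction below that interval.

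On stakes, section 5.4.1.3 says "Thus, our follow-up analysis will be descriptive", and section 5.1.1.3 says the post-initiation exploratory analysis will not feed directly into the cost-effectiveness model. Section 4's remark that less frequent dosing could matter for cost-effectiveness concerns reduction after six attack-free months. A direct effect of this flaw on the model is therefore not supported. Finally, a separate analysis plan could name a denominator, but the entry criterion is fixed in the protocol.

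**Conclusion.** The point holds. The dose reduction cohort selects against early reducers, and no other cohort or table row in the protocol measures them. With a cut-off of 16 days or less, none can be both admitted and identified by the Annex 2 rule before day 180. At cut-offs of 17 to 21 days some are, but among patients otherwise on schedule the early share is still biased downward. These results assume on-schedule injections and a single sustained change. The percentages also assume evenly spread change days and are illustrative; the direction does not depend on that spread. The figure for the cohort (Figure 2) was not available to check. Severity is moderate: one descriptive sub-question of an exploratory objective is affected, and the percentage reducing after six months is affected only through the undated late changes and the missing tolerance.

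**What to change.** - In section 5.1.1.4, count early reduction among all Takhzyro initiators who meet the entry-date, washout and existing 270-day enrolment criteria, before the two-weekly criterion is applied. Enrolment to day 180 alone would not be enough, because changes after day 126 could not yet meet the 90-day rule.
- Apply the Annex 2 rule across the full 270 days. Date the change by the first lengthened interval, not by the start of the 90-day window. Require continued dispensing afterwards, so that refill gaps and discontinuation are not counted.
- Keep the two-weekly criterion, with a stated numerical tolerance, only for the percentage reducing after six months attack free. Report how many patients it removes.
- Reconcile the Table 4 titration row with section 4 and Annex 1. Once reworded, it can carry the early-reduction result.

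The cost is a few sentences, one reworded table row and slightly more analysis on the same data. Some non-adherence may still be counted as titration, and the report should say so.

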Annex 3: Results Table Shells

Table 1: Baseline characteristics of patients with HAE

Characteristic	RWE results	Notes	Prior ICER review base case	Prior ICER review source
Mean age			39.63	Banerji et al. 2017, ³⁰ Longhurst et al. 2017, ³¹ Zuraw et al. 2010 ³²
Female, %			68.4%	Banerji et al. 2017, ³⁰ Longhurst et al. 2017, ³¹ Zuraw et al. 2010 ³²
Mean weight, females			76.4	Fryar et al. 2016 ³³
Mean weight, males			88.8	Fryar et al. 2016 ³³
List of top 10 non-HAE therapies (therapeutic class)				

Table 2: Attack rates, utilization, and costs in the six-month baseline period before initiation of prophylaxis treatment

Characteristic	RWE results	Notes	Prior ICER review base case	Prior ICER review source
ATTACK RATES AND TREATMENTS ADMINISTERED				
Mean attack rate per month (HAE-specific severe and non-severe)			3.39	Banerji et al. 2017, ³⁰ Longhurst et al. 2017, ³¹ Zuraw et al. 2010 ³²
Number of patients who are attack free in baseline period before starting prophylaxis therapy		Due to drug indications and health plan requirements, this is expected to be minimal or 0.	-	

Distribution of severe attack free months			-	
Proportion of attacks, by severity				
Severe - HAE specific			-	
Severe - All-cause			-	
Non-severe			-	
Treatment administered – Non-severe attacks				
Self			64.9%	Riedl et al, 2015 ³⁴
Home nurse			13.8%	Riedl et al, 2015 ³⁴
Outpatient			21.3%	Riedl et al, 2015 ³⁴
% of severe-HAE specific attacks resulting in hospitalization			40.9%	Zilberberg et al 2011a ³⁵
% of hospitalized patients receiving cricothyrotomy/tracheotomy			40.0%	Bork et al ³⁶
% of cricothyrotomy/tracheotomy patients who receive artificial respiration			40.0%	Bork et al ³⁶
% of hospitalized patients who are intubated			60.0%	Bork et al ³⁶
% of intubated who receive artificial respiration			26.7%	Bork et al ³⁶
% of attacks treated with these on-demand drugs				Assumption in model
Berinert			25%	
Kalbitor			25%	

Firazyr			25%	
Ruconest			25%	
BASELINE HAE-SPECIFIC COST OUTCOMES				
Costs per home nurse			\$179	Graham et al 2017 ³⁷
Costs per physician office visit			\$266	Graham et al 2017 ³⁷
Costs per ED visit			\$1,796	Zilberberg et al 2011a and 2011b ^{35,38}
Costs per hospitalization			\$5,782	Zilberberg et al 2011a and 2011b ^{35,38}
BASELINE HAE-SPECIFIC UTILIZATION OUTCOMES				
Average number of home visits			-	
Average number physician office visits			-	
Average number of ED visits			-	
Average number of hospitalizations			-	

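### Table 4 does not report the Takhzyro step-down percentage that the methods promise, because attack-free status and every-4-week dosing are never crossed

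*Protocol*

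**What the plan says.** Section 4 of the Protocol asks, under the exploratory objective, what share of Takhzyro patients move to less frequent dosing once they have been attack free for six months. Section 5.1.1.4 repeats this for the dose reduction cohort: "we will determine the percent of patients that receive the less frequent dosing regimen after six months attack free".

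The same section sets the cohort. Entry runs from 23 August 2018 to 5 July 2019, with at least 270 days of enrolment afterwards (six months plus 90 days for the new regimen to show), and "patients will be required to have dosing, on average, every two weeks during the 180 days post cohort entry". Freedom from attacks is not an entry condition. Annex 2 classifies dosing as every four weeks when the total dose is at most 1200 mg over a 90-day period.

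Table 4 in Annex 3 has three rows:

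- Row 1, on attacks, is labelled "Percent of Takhzyro patients attack free for 6-month period".
- Row 2, on the reduced regimen, is labelled "Percent patients on every 4-week dosing for 6 months".
- Row 3, on changes of dose, is labelled "Percent of patients that titrated down to every 2-week dosing".

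The Notes column is empty, and no row gives a numerator or denominator.

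**The concern.** The promised quantity joins two facts about the same patient: attack free for six months, then dosed every four weeks. Table 4 shows each fact only as an overall percentage. Filled in as written, it would not separate patients who stepped down after six attack-free months from patients whose dosing fell although they still had attacks. That distinction is what the study question asks about, and section 4 lists the real-world step-down proportion among the uncertainties that motivate the work and says that it could affect incremental cost-effectiveness.

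The other rows do not close the gap. The third names the regimen on which patients start, so nobody in this cohort can titrate down to it. The second asks for a duration on the reduced dose that the cohort's minimum follow-up does not cover.

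**Working it through.** **1. The plan's own date.** Inputs: last entry 5 July 2019 and 270 days of follow-up (section 5.1.1.4); end of data 31 March 2020 (section 5.1.1.3). 5 July 2019 + 270 days = 31 March 2020, an exact match. The cohort is therefore built for 180 days of every-2-week dosing followed by 90 days in which to observe the new regimen.

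**2. Rows against the promise.**

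| Table 4 row | What it gives | Limited to attack-free patients? |
|---|---|---|
| 1 | overall share attack free | it defines the group but says nothing on dosing |
| 2 | overall share on every-4-week dosing | no |
| 3 | share moved to the starting regimen | no |

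Row 2 cannot safely be read as nested under row 1. Where Annex 3 intends a nested denominator it writes it out, as in Table 2's percentage "of intubated who receive artificial respiration". Cohort entry does not supply the restriction either.

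**3. Can the figure be derived from rows 1 and 2?** Let A be the share attack free, D the share on every-4-week dosing, and J the share with both. Then max(0, A + D − 1) ≤ J ≤ min(A, D), and step-down among attack-free patients is J/A. The Protocol gives no values for A or D, so those below are assumptions for illustration. The last column adds a further assumption, that at least 80% of those who step down are attack free, so that J ≥ 0.8D.

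| A | D | J | J/A | J/A if J ≥ 0.8D |
|---|---|---|---|---|
| 0.50 | 0.30 | 0 to 0.30 | 0% to 60% | 0.24/0.50 = 48% to 60% |
| 0.60 | 0.30 | 0 to 0.30 | 0% to 50% | 0.24/0.60 = 40% to 50% |
| 0.70 | 0.40 | 0.10 to 0.40 | 14% to 57% | 0.32/0.70 = 46% to 57% |

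The two rows fix neither J nor J/A. The point therefore stands whether the promised percentage is read as a share of the whole cohort (J) or of attack-free patients (J/A).

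**4. Row 2's duration.** Because the first 180 days must average every-2-week dosing, six months on the reduced dose needs about 180 + 180 = 360 days. For the last entrant, 5 July 2019 + 360 days = 29 June 2020, which is 90 days past the end of data. The latest entry date that could reach 360 days is 31 March 2020 − 360 days = 6 April 2019. Entrants in the last 90 of the 316 days between 23 August 2018 and 5 July 2019 (90/316 = 28% of calendar time, not of patients) cannot satisfy row 2 as worded. The Annex 2 rule does fit the guaranteed follow-up: 1200 mg is four 300 mg injections, against 90/28 = 3.2 expected at every four weeks and 90/14 = 6.4 at every two weeks.

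**5. Severity of attack.** Table 3 specifies severe attacks ("Distribution of severe attack free months"), whereas Table 4 and section 5.1.1.4 do not. Section 5.4.1.3 restricts follow-up attack rates to severe attacks, in a sentence about rates stratified by the three drugs. It does not mention the dose reduction cohort.

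**The case against.** The strongest defence is that the methods text governs. Sections 4 and 5.1.1.4 name the right quantity, both variables are available for each patient, and nothing says that the shells are exhaustive. An analyst who followed section 5.1.1.4 would compute the figure, and row-level denominators are often left to an analysis plan that is not shown here. This answers any inference that the figure cannot be computed or would be biased. It does not remove the mismatch: Table 4 is the only shell for this analysis, the Protocol itself fixes its rows, and none of them is the promised quantity. Two of the rows are also worded wrongly in their own right.

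A reader might infer that attack free is undefined throughout the Protocol. That goes too far. The severe-only rule in section 5.4.1.3 sits under the same exploratory objective and is a natural reading for Table 4. The payer rule in Annex 4, which turns on the absence of acute attacks, is coverage background and does not define a study outcome. What remains is a small clarification.

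The ranges are also open to challenge, and fairly. They come from invented inputs and show only that two overall percentages do not determine a joint one. The 0% ends would need every step-down to occur in patients who still had attacks, which is unlikely given the label and the payer policy.

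**Conclusion.** The point holds in a limited form. Table 4 does not report the step-down percentage that sections 4 and 5.1.1.4 promise, its every-4-week row asks for longer than the follow-up guarantees, and its third row names the wrong regimen. These conclusions rest on the Protocol's text and dates alone. The size of the gap in step 3 of the working depends wholly on assumed inputs and predicts nothing about this cohort.

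A reader might infer that the cost-effectiveness results are at risk. The document does not support that: the output is exploratory and descriptive, and section 5.1.1.3 says that the post-initiation exploratory analysis will not directly feed the model. The harm is that the table leaves the study's own question unanswered. The shell should be corrected, but no primary result depends on it.

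**What to change.** In Table 4:

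- Add a row giving n/N and percent for every-4-week dosing (at most 1200 mg over the 90 days after day 180, by the Annex 2 rule) among patients attack free in days 1 to 180. Show counts, because cells will be small. With the cohort total also shown, n gives the whole-cohort share as well.
- In row 2, replace the six-month duration with the 90-day window that the 270-day follow-up supports.
- In row 3, change every-2-week to every-4-week dosing. It will then overlap with row 2, so either say what distinguishes it or use it as the place for the crossed percentage.
- In the Notes column, state whether the severe-only rule of section 5.4.1.3 applies to attack free here and, if so, which of the two severe definitions in section 5.2.1.4 is used.

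A further row for every-4-week dosing among patients with at least one attack would be informative but is optional, since the Protocol does not promise it. The cost is one row, two wording changes and a note. All the variables are already planned and no new data are needed. The only drawback is small cells in an exploratory table.
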